2.2 Study objectives

The objective of this open, prospective, controlled, multicentre, non-interventional cohort study (NIS) is to record the treatment compliance (measured as persistence and adherence) of patients treated with dabigatran etexilate or VKA.

Primary study objective:

- To compare persistence in patients treated with dabigatran etexilate or VKA.

Secondary study objectives:

- To compare adherence in patients treated with dabigatran etexilate or VKA
- To record the reasons for any treatment discontinuation

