7.3 Planned analyses

The evaluation is performed using SAS® software. All analyses are descriptive. For end-of-text tables, N / mean / SD / min / median / max are given as statistical characterisation measures for constant variables; for categorial variables, N / % per category are given.

All patients documented in the CRF with at least one prescription for dabigatran etexilate or VKA and who meet the inclusion criterion (main diagnosis: non-valvular AF) are included in the analyses (i.e. “all eligible patients”). For the analysis of adverse events, all patients documented in the CRF with at least one prescription for dabigatran etexilate or VKA will be included in the analyses. In order to allow a valid comparison of compliance (persistence and adherence), a 1:1 matching of patients prescribed dabigatran or VKA will be performed based on the exposure propensity score (PS). The propensity score is calculated on the basis of a logistic regression model in which the choice of treatment is included in the model as a dependent variable and further relevant baseline characteristics are considered as independent variables in the model. The relevant baseline characteristics included in the PS model will be predefined in the analysis plan. The choice is based on the premise that all baseline variables for which a priori an association with persistence and/or adherence is expected are to be

included. These variables correspond to the potential confounder variables for a comparative analysis.

Baseline patient characteristics

The cohort resulting from the 1:1 matching as well as the whole cohort of all eligible patients will be characterised, stratified by treatment group, in terms of demographic data, concurrent diseases, concomitant medication, data on AF severity and other baseline characteristics (including risk score for stroke and bleeding, i.e. CHADS-VASc and HAS-BLED).

Persistence and reasons for treatment discontinuation

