is performed according to Morisky. For patients who have not answered one or more questions, this score is not calculated. If the proportion of patients with missing answers is high (e.g. >20%), a sensitivity analysis will be performed, in which the score will also be

calculated if up to 2 questions per patient are missing²³. Patients who at the time of the visit are no longer on the initial therapy and those who have already discontinued the study before this time will be described separately from those for whom the Morisky score cannot be calculated for other reasons. Patients with missing values are analysed in terms of their baseline characteristics in comparison with patients with an evaluable Morisky score; patients with missing values will be stratified into the above-mentioned groups of study drop-outs, treatment drop-outs and patients with missing values for other reasons and the analysis will only be performed for strata with at least 200 patients (total and per treatment group).

The number and proportion of patients who fall into the different adherence classes will be presented for the dabigatran and VKA patients.

Coding

The current version of the Medical Dictionary for Drug Regulatory Activities will be used for coding adverse events. Concomitant medication will be coded using the current version of the WHO-DD.

Analysis of safety endpoints

For the analysis of adverse events, all patients documented in the CRF with at least one prescription for dabigatran etexilate or VKA will be included. Analyses of adverse events are descriptive and will be performed in accordance with Boehringer Ingelheim standards. In the analysis of adverse events, the focus is on treatment-emergent events. Events that occur in the period between the start of treatment and the permanent discontinuation of treatment or the end of the study (in patients in whom no permanent discontinuation of the medication is documented in the course of the study) + 6 days are categorised as treatment emergent and will be presented in frequency tables for dabigatran and VKA patients.

Adverse events that occur before or after this period will be assigned to “screening” or “post-treatment” and only presented in listings.

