the power for a descriptive p value ≤ 0.05 in a 2-tailed test for the same persistence rates is as follows (dependent on the VKA persistence rate):

Assumed VKA persistence rate*	51%	53.8%	56.5%
Power	97.8%	84.8%	61.1%

* The calculations were performed with ADDPLAN6 and are based on survival time analysis test statistics and the endpoint variables "Time to permanent treatment discontinuation".

Reasons for change 3:

After 6 months of site and patient recruitment it became evident that the targeted patient and site numbers will not be met and that recruitment time should be longer.

Therefore the planned patient number will be reduced to 1600 and site number to 800.

Observational Plan

Non-interventional study

Local Amendment

Local Amendment Number:	Local Amendment 2			
Country	Germany			
Date:	04. JAN 2016	 To be implemented only after documented approval of the IRB / IEC / Competent Authorities		
EudraCT No.:	n.a.	 To be implemented immediately in order to eliminate hazard – IRB / IEC / Competent Authority to be notified of change with request for approval		
BI Trial No.:	1160.218			
Investigational Product(s):	Pradaxa®	 Can be implemented without IRB / IEC / Competent Authority approval as changes involve logistical or administrative aspects only		
Title:	Drug persistence/adherence in patients being treated with Pradaxa® (dabigatran etexilate) or vitamin K antagonists (VKA) for stroke prevention in non-valvular atrial fibrillation (AF)			
Rationale for Local Amendment:	
After 15 months of patient recruitment 1050 / 1600 patients have been included until December 2015. For a meaningful data analysis and interpretation, the targeted patient number of 1600 patients should be met.
 
Therefore, recruitment time will be prolonged for one more year to 27 months (LPI December 2016), thus study duration will also increase. LPO is now planned for December 2017.
 
Other timelines will change accordingly.
 
In case 1600 patients will be included earlier, recruitment may be stopped before December 2016.
 
As this amendment is administrative and does not change the content or the nature of this non-interventional study, for readability reasons we refrain from changing every sentence in which site numbers, patient numbers or timelines are mentioned, except for the front page, study synopsis and statistics section.
			
Page 1 of 3				

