7. PLANNED ANALYSIS

All analyses in this study are descriptive; results are to be interpreted in an explorative manner.

For categorical variables summary tabulations of the number and percentage within each category (with a category for missing data) of the parameter will be presented. For continuous variables N, mean, SD, minimum, median, maximum and number of missing values will be presented. To achieve a valid comparability of compliance (persistence and adherence) patients prescribed to dabigatran etexilate or VKA will be matched 1:1 based on the Exposure Propensity Score (PS) and caliper matching with caliper of width equal to 0.2xStandard deviation of PS.

The Propensity Score will be calculated based on a logistic regression model taking the choice of treatment as dependent variable and baseline characteristics as independent variables into account. All baseline variables with an a priori association to persistence and adherence will be included into the regression analysis.

These variables correspond to the potential cofounder variables for a comparative analysis.

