7.4 PRIMARY ENDPOINT(S)

The analysis of the primary endpoint will be based on the patient cohort resulting from the 1:1 matching. Time until termination of treatment will be presented for both treatment groups (Dabigatran etexilate vs. VKA) by Kaplan-Meier estimates and displayed graphically, respectively. Especially for time points 3, 6, 9 and 12 months Kaplan-Meier estimates for persistence will be calculated.

The comparison of persistence between the treatments with dabigatran etexilate versus VKA will be conducted by means of the stratified Log-rank test, which takes dependencies resulting from the matching of the treatment groups into account. Patients who discontinue

study prematurely and without documented treatment discontinuation will be censored at study termination. Patients completing the study as planned will be censored at the day after last visit, if no earlier treatment discontinuation is documented. Association between patient characteristics (incl. method of treatment) and persistence will be determined by means of cox regression (univariate and multivariate model). First, univariate regression for each of the independent variables will be performed. Afterwards, all covariates will be entered into a stepwise multivariate regression. The entry level will be $p=0.5$ and the stay level $p=0.1$. Baseline characteristics will be presented stratified by patients who discontinued the study prematurely versus no discontinuation.

A multivariate Cox Regression model (including factors for the calculation of the propensity score and the choice of treatment) will be used as sensitivity analysis. All patients, who are within the “common support” of the empiric PS density function (instead of the matched pairs), will be included in this analysis. The “common support” will be determined after patients with a propensity score above the 97.5% percentile and below the 2.5% percentile have been excluded for each treatment group, respectively. This will be done to avoid high influence of patients with extreme PS.

The following covariates will be used –depending on the sample size- for the Propensity Score Matching and the sensitivity analysis

- CHA₂DS₂-VASC Score (<2, ≥ 2)
- HAS BLED-Score (<3, ≥ 3)
- Age at registration (<65, 65-<75, ≥ 75)
- Previous stroke (Yes, No)
- Treatment (VKA, Pradaxa[®]) (sensitivity analysis only)

and the following covariates will be used –depending on the sample size- for the Cox regression

- CHA₂DS₂-VASC Score (<2, ≥ 2)

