7.5 SECONDARY ENDPOINT(S)

Absolute number and percentage of patients, who discontinue the initial treatment during study, will be summarized collectively and according to reasons for discontinuation for the dabigatran etexilate and VKA cohort, respectively.

The analysis of secondary endpoints will be based on the patient cohort resulting from the 1:1 matching.

The Morisky questionnaire consists of 8 question and will be answered at the 6- months visit. Each question can be scored with 0 or 1. For questions 1-7, 'no' will be scored with 0 and 'yes' with 1. For question 8, 'None/rarely' will be scored with 0 and all other answers with 1. The Morisky score is given by the sum of the values of each question, which implies a score between 0 and 8.

The categorisation of patients into low adherence (score >2), medium adherence (score=1,2) and high adherence (score=0) is done according to Morisky. The score will only be calculated for patients who answered all eight questions. In case that the proportion of the patients who did not answers all questions is too high (i.e. >20%) a sensitivity analysis will be conducted in which the score will be calculated if up to 2 questions per patient are missing. Patients who changed their initial treatment or withdrew from the study before the 6-months visit, will be displayed seperately from those for which the Morisky score could not be calculated for other reasons. Patients with missing data will be analyzed regarding to their baseline characteristics in comparision to the patients with an evaluable Morisky score; patients with missing values at the 6-months visit will be stratified into (i) the groups of study drop-outs, (ii) treatment drop-outs and (iii) patients with missing values because of other reason. The last mentioned analyses will only be done for strata of at least 200 patient (overall and for each treatment group).

Number and percentage of patients within the different adherence classes will be displayed for dabigatran etexilate and VKA patients, respectively. Furthermore the following subgroups will be presented for adherence (overall and for each treatment group):

- CHA₂DS₂-VASc-Score (<2, ≥2)
- Age (<65, 65- <75, ≥75)
- Previous stroke Yes, No)
- Medical specialty of attending physician (Internist, Cardiologist, General practitioner, Other)
- Daily dose of Pradaxa® at initial visit (2x110mg daily, 2x150mg daily) [Patients treated with Pradaxa® only]
- HAS-BLED-Score (<3, ≥3).

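### Comparing adherence between the drugs is an objective, but the plan only tabulates percentages per arm, with no between-arm difference or confidence interval

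*SAP*

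**What the plan says.** Among the secondary objectives, Protocol 2.2 lists: "To compare adherence in patients treated with dabigatran etexilate or VKA". Protocol 7.3 introduces the 1:1 propensity matching with the words "In order to allow a valid comparison of compliance (persistence and adherence", and SAP section 7 gives the same reason. Adherence is therefore one of the two comparisons that the matching is meant to support.

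For the result itself, Protocol 7.3 says: "The number and proportion of patients who fall into the different adherence classes will be presented for the dabigatran and VKA patients". SAP 7.5 repeats this: "Number and percentage of patients within the different adherence classes will be displayed for dabigatran etexilate and VKA patients, respectively". It adds the same display by subgroup and fixes the analysis set: "The analysis of secondary endpoints will be based on the patient cohort resulting from the 1:1 matching".

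SAP 7.5 shows patients who changed treatment or left the study before month 6 separately, and requires all eight answers for a score. Neither document says what happens to a matched patient whose partner has no score.

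Persistence is handled differently. SAP 7.4 states: "The comparison of persistence between the treatments with dabigatran etexilate versus VKA will be conducted by means of the stratified Log-rank test". It also plans Cox models and a covariate-adjusted sensitivity analysis within common support.

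Both endpoints have the same status under SAP section 7: "All analyses in this study are descriptive; results are to be interpreted in an explorative manner".

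**The concern.** An objective to compare needs at least an estimate of the contrast and a measure of its uncertainty. As planned, the reader gets two columns of percentages and must judge the gap by eye. Nothing shows whether a gap of several points is more than sampling error, and the documents give no precision figure for adherence. The only power figures, in Protocol 7.5 as revised by Local Amendment 1, are for persistence.

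A second issue concerns the matching. It is done at baseline, but the score exists only for patients still on the initial drug and in the study at month 6. The planning rates assume that retention on treatment differs by arm. The scored patients are then a subset selected by persistence, and the plan does not say how the matching is to be carried through to them.

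**Working it through.** **Inputs from the plan (Protocol 7.5 as replaced by Local Amendment 1, Change 3)**
- 800 patients per arm; 66% of VKA patients matched
- 12-month persistence: 63% for dabigatran; 51%, 53.8% or 56.5% for VKA
- 15% drop-outs or missing values after one year

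**Assumptions not in the documents**
- Constant hazards, because no 6-month rates are given
- Independence within pairs
- The 15% counted wholly as study drop-out, on top of treatment discontinuation
- 50-70% of scored patients with high adherence

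**Step 1: the plan's own figure.** 800 × 0.66 = 528 pairs, and 528 × 2 = 1056 patients. This agrees with the amendment.

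**Step 2: patients who could have a score at month 6.** Share = √(12-month persistence × 0.85).

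| Arm | Calculation | Share | Of 528 |
|---|---|---|---|
| Dabigatran, 63% | √(0.63 × 0.85) | 73.2% | 386 |
| VKA, 51% | √(0.51 × 0.85) | 65.8% | 348 |
| VKA, 53.8% | √(0.538 × 0.85) | 67.6% | 357 |
| VKA, 56.5% | √(0.565 × 0.85) | 69.3% | 366 |

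Leaving study drop-out aside, √0.63 = 79% of dabigatran and √0.51 to √0.565 = 71-75% of VKA patients would still be on treatment.

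**Step 3: intact pairs.** The product of the two shares is 0.732 × 0.658 = 48.2%, 0.732 × 0.676 = 49.5%, or 0.732 × 0.693 = 50.7%. That is about 254 to 268 of 528 pairs, so 49-52% are incomplete.

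**Step 4: how far this depends on the assumptions.** Incomplete pairs, changing one assumption at a time:

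| Change | Incomplete pairs |
|---|---|
| One third of discontinuations by month 6 | 36-38% |
| No study drop-out | 40-43% |
| Within-pair correlation 0.1-0.2 | 45-50% |
| Linear discontinuation | 46-48% |
| Two thirds of discontinuations by month 6 | 55-57% |
| All 15% lost by month 6 | 57-59% |

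A further 10-20% of patients with unanswered items would give 59-69%. Because the 15% already includes some missing values, that step may count part of the loss twice.

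**Step 5: precision of a difference in high adherence.** Half-width = 1.96 × √[p(1−p)(1/n₁ + 1/n₂)].
- p = 0.5, n = 386 and 348: 1.96 × √[0.25 × (1/386 + 1/348)] = 7.2 points
- p = 0.7, n = 386 and 348: 1.96 × √[0.21 × (1/386 + 1/348)] = 6.6 points
- n = 386 and 366: 7.2 and 6.6 points again (0.0715 and 0.0655)
- All 528 per arm, for comparison: 6.0 and 5.5 points

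The formula ignores any within-pair correlation; a positive correlation would narrow the interval somewhat.

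**The case against.** **The study is declared descriptive.** There are no confirmatory hypotheses, the secondary endpoint is defined as the proportion per class stratified by drug, and Protocol 7.1 links matching and adjustment to persistence, the primary variable. This stands as far as it goes: the absence of a hypothesis test for adherence is no error. But an estimated difference with an interval is itself descriptive. Persistence has the same status and still gets a between-arm comparison, and Protocol 7.3 names adherence as a purpose of the matching.

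**Broken pairs do not mean unbalanced groups.** A reader might infer that the scored groups are unbalanced because half the pairs are broken. The documents do not support that. Propensity matching balances group distributions; losing partners produces imbalance only if the loss depends on covariates and acts differently by arm. At the plan's persistence rates, take a binary covariate with 20% or 50% prevalence (assumed). If it doubles the discontinuation hazard in both arms, the standardised difference among patients still on drug at month 6 is only about 0.02-0.04; if it triples the hazard, about 0.03-0.06. Larger imbalance would need something more, such as arm-specific effects. This objection stands.

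**One half is not a figure from the plan.** It is a projection, and the 15% may already cover some missing questionnaires. This stands too.

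**The plan has safeguards.** SAP 7.5 shows adherence by arm within levels of all four propensity covariates, and compares patients with and without a score at baseline. The subgroup tables help, but they give neither an overall contrast nor an interval. The comparison of missing patients is limited to strata of at least 200. Under the assumptions above, treatment drop-outs by month 6 number about 105 for dabigatran and 126-145 for VKA, and study drop-outs about 35-37 per arm. Neither group reaches 200 within an arm.

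**Conclusion.** The gap is real and can be read directly from both documents: a comparison of adherence is promised, and no between-arm difference or interval is planned. Its practical size is a margin of about ±7 points on a difference in high adherence. That figure rests on the amended planning rates, constant hazards and an assumed 50-70% with high adherence. Unless the margin is reported, readers could take a chance gap of that size for a real one.

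The loss of pairing is a secondary matter. Roughly half the pairs intact is a projection, and the plan should say how patients without a scored partner are treated. Balance among scored patients is not guaranteed, given the assumed difference in retention, but nothing in the documents shows that it fails. For a secondary objective in an exploratory study, the change is worth making but is not critical.

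**What to change.** In SAP 7.5, keep the tables and add:

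1. The between-arm difference in the proportion with high adherence, with a 95% CI, among scored patients of the matched group. Use robust variance clustered on the pair, and keep patients whose partner has no score. This retains the prescribed analysis set.
2. As a sensitivity analysis, the same difference adjusted for the propensity-score covariates in all scored patients within common support, mirroring the persistence sensitivity analysis in SAP 7.4.
3. A statement that both estimates are descriptive and conditional on remaining on the initial drug and in the study at month 6. Adjustment for baseline covariates does not remove selection on unmeasured causes of persistence.

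A proportional-odds model over the three classes is not needed to close the gap and would add an assumption. The cost is some SAP wording and a little more analysis work; no new data are required.

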7.6 FURTHER ENDPOINT(S)

This section is not applicable as no further endpoint has been specified in the protocol.

7.7 EXTENT OF EXPOSURE

For duration of treatment see section 7.4. In addition, the duration of treatment with Viramune® will be given for the Treated Set with the number of patients and percentage in the following categories of duration:

<4 weeks, 4 - <10 weeks, 10-<30 weeks, 30-<50 weeks, 50-<70 weeks, ≥70 weeks.

In addition, the total treatment time of all patients will be provided in years.

Further on, the dosage of Pradaxa® at initial visit, which could be 2x110mg daily or 2x150mg daily, will be displayed (Section 7.1) as well as changes in dosage for the Treated Set.

7.8 SAFETY ANALYSIS

The analysis of adverse events will be descriptive and conducted according to Boehringer Ingelheim standards. The main focus will be on treatment emergent events. All AE that occurred between start of treatment and six days after permanently discontinuation of therapy or end of study will be considered as treatment emergent and will be displayed in frequency tables for dabigatran etexilate and VKA treated patients, respectively. Non-treatment-emergent events will be assigned to “screening” or “post-treatment” and only be displayed in listings. All analyses will be based on the safety population.

Frequency, severity and causality of treatment-emergent AEs will be tabulated according to MedDRA-SOC and PT. Treatment-emergent SAEs will be tabulated as well as adverse events leading to treatment discontinuation.

Unless otherwise specified, the analyses of adverse events will be descriptive in nature. All analyses of AEs will be based on the number of patients with AEs and not on the number of AEs, except the analyses of action taken and the analysis of reason for serious TEAE.

An overall summary of adverse events will be presented.

The frequency of patients with adverse events will be summarised by treatment, primary system organ class and preferred term (mention MedDRA levels to be displayed in the tables). Separate tables will be provided for patients with serious adverse events. An additional table will be done for all non-serious adverse events with a frequency of more than 5%.

The system organ classes will be sorted alphabetically, preferred terms will be sorted by frequency (within system organ class).

For analysis multiple AE occurrence data on the CRF will be collapsed into an AE event provided that all of the following applies:

- All AE attributes are identical (PT, NCI grade, action taken, therapy required, seriousness, reason for seriousness, relationship, outcome)

Proprietary confidential information © 2015 Boehringer Ingelheim International GmbH or one or more of its affiliated companies

- The occurrences were time-overlapping or time-adjacent (time-adjacency of 2 occurrences is given if the second occurrence started on the same day or on the day after the end of the first occurrence). For classification into TEAE or Non-TEAE, the first documented start of event will be used.

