7.1 Statistical design model

This is a non-randomised, open, multicentre, non-interventional cohort study with patients who are suffering from non-valvular atrial fibrillation and have recently been prescribed an oral anticoagulant (VKA or dabigatran etexilate). As the treatment is attributed by the doctor, differences in patient characteristics between the two patient groups receiving VKA or dabigatran treatment that are to be compared may be expected. To improve the comparability of the treatment groups and hence increase the internal validity, the analysis of the primary target variable (persistence) is planned using methods such as matching or trimming of the population and adjustment.

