6.3 PATIENT SETS ANALYSED

Treated Set (TS): All patients with at least one documented prescription of dabigatran etexilate or VKA.

Full Analysis Set (FAS): All patients from the Treated Set with main diagnosis non-valvular atrial fibrillation and who have at least one evaluable efficacy endpoint.

Matched group (MG): Patient cohort resulting from the 1:1 matching based on FAS.

Table 6.3: 1 Patient sets analysed

Class of endpoint	TS	MG
Primary and secondary endpoint		X
Safety endpoints	X	
Demographic/baseline	X	X

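### Adverse events are tabulated by drug in the unmatched Treated Set only, so differences in patient mix can appear as differences between drugs when the tables are read side by side

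*SAP*

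**What the plan says.** - **Display.** SAP 7.8 states that treatment-emergent AEs "will be displayed in frequency tables for dabigatran etexilate and VKA treated patients, respectively". It adds: "The frequency of patients with adverse events will be summarised by treatment, primary system organ class and preferred term". Serious AEs and AEs leading to discontinuation are also tabulated.
- **Population.** SAP 7.8 says: "All analyses will be based on the safety population". SAP 6.3 defines no set of that name. Table 6.3: 1 ticks safety endpoints for the Treated Set only, and that set is defined as "All patients with at least one documented prescription of dabigatran etexilate or VKA". Protocol 7.3 agrees: "For the analysis of adverse events, all patients documented in the CRF with at least one prescription for dabigatran etexilate or VKA will be included".
- **Expected differences.** Protocol 7.1 notes that the doctor assigns treatment, so "differences in patient characteristics between the two patient groups receiving VKA or dabigatran treatment that are to be compared may be expected".
- **Where patient mix is handled.** Protocol 7.1 plans matching or trimming and adjustment for persistence. Protocol 7.3 and SAP 7 extend matching to adherence, and SAP 7.5 to reasons for discontinuation. SAP 7.4 lists the matching covariates, subject to sample size: CHA2DS2-VASc (2 classes), HAS-BLED (2 classes), age (3 classes) and previous stroke (yes/no).
- **Baseline.** SAP 7.1 and 7.2 show baseline data and concomitant diseases and medication for both the matched cohort and the Treated Set; SAP 7.1 gives baseline by treatment group.

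The available text contains no matched, stratified, weighted or adjusted AE analysis.

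**The concern.** The matching covariates describe stroke risk, bleeding risk and age. In anticoagulated patients these may well be related to AE frequency too. The plan treats them as confounders when it compares persistence and adherence, but leaves them out of account where it places AE percentages for the two drugs next to each other.

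Readers tend to compare such columns, whatever the label. If one drug is given more often to patients at higher risk, its column can look worse with no drug effect. The opposite pattern can hide a real excess.

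There is also an internal mismatch. Protocol 6.1 counts intolerable AEs among the reasons for discontinuation, and SAP 7.5 analyses those reasons in the matched cohort. SAP 7.8 tabulates AEs leading to discontinuation in the Treated Set. The report could show two different pictures of nearly the same quantity, with no statement of which one supports a comparison.

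**Working it through.** **1. The plan's own figure.** Local Amendment 1, Change 3 assumes 800 patients per drug and a matching partner for 66% of VKA patients.

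- Matched N = 2 × 0.66 × 800 = 1056, as stated.
- Patients in the AE tables without a partner = 1600 − 1056 = 544, and 544 / 1600 = 34%.

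The 66% is a sample-size assumption, not an estimate of imbalance.

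**2. The largest imbalance in one factor that fits 66%.** Treat each group as 66% matched and 34% unmatched, with the same share of high-risk patients in the two matched parts. The gap in that share is 0.34 × (u1 − u2), where u1 and u2 are the high-risk shares among the unmatched patients. Its maximum is 34 percentage points. Placed symmetrically this is 67% v 33% (overlap 2 × 0.33 = 0.66). It is the extreme case: all the non-overlap falls on one binary factor that also drives AEs.

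**3. Crude risk ratio with no drug effect.** Let high-risk patients have k times the AE risk of the others; k is assumed.

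Ratio = (0.67k + 0.33) / (0.33k + 0.67)

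- k = 1.25: 1.1675 / 1.0825 = 1.08
- k = 1.5: 1.335 / 1.165 = 1.15
- k = 2: 1.67 / 1.33 = 1.26

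The ratio also depends on where the gap sits. With 34% v 0% and k = 2 it is 0.34 × 2 + 0.66 = 1.34. So 67% v 33% is extreme in the gap, but is not a bound on the ratio.

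**4. Other assumed mixes.** The AE risk is 5% in low-risk and 15% in high-risk patients on both drugs, with 800 patients per drug. All figures are assumed.

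| High-risk share | Crude AE risk | Patients with AE | Ratio |
|---|---|---|---|
| 30% v 30% | 8.0% v 8.0% | 64 v 64 | 1.00 |
| 25% v 35% | 7.5% v 8.5% | 60 v 68 | 1.13 |
| 20% v 40% | 7.0% v 9.0% | 56 v 72 | 1.29 |
| 20% v 50% | 7.0% v 10.0% | 56 v 80 | 1.43 |

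With risks of 5% and 10% instead, the last three ratios are 1.08, 1.17 and 1.25.

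**5. What matching would not remove.** The amended plan assumes 12-month persistence of 63% on dabigatran and 51% to 56.5% on VKA. With exponential discontinuation (assumed) and no dropout, mean time on treatment in the year is (1 − p) / (−ln p):

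- 63%: 0.37 / 0.462 = 0.80 years
- 56.5%: 0.435 / 0.571 = 0.76 years
- 51%: 0.49 / 0.673 = 0.73 years

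On these figures the on-treatment window is about 5% to 10% longer on dabigatran (0.801 / 0.762 = 1.05; 0.801 / 0.728 = 1.10), even in a perfectly matched cohort.

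**The case against.** The strongest reply is that no safety comparison is planned. The objectives are persistence, adherence and reasons for discontinuation. The AE analysis is called descriptive, with no test, risk ratio or between-drug statement. This stands in part: the problem is the risk of misreading tables, not an invalid test. But persistence is equally descriptive under Protocol 7, and the plan still matches there. A descriptive label removes the test, not the confounding.

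Second, safeguards exist. Only patients eligible for both drugs are included (Protocol 3.3.1 and 3.3.2), baseline is shown by drug for the Treated Set, and discontinuation reasons are already analysed in the matched cohort. These points stand, and they narrow or reveal an imbalance. They do not correct the AE percentages, and Protocol 7.1 still expects differences. Alternating inclusion (Protocol 4.1.2) is there to equalise group sizes, not patient mix.

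Third, the matched cohort is an imperfect safety set. It has about 1056 of 1600 patients. It comes from a Full Analysis Set that requires an evaluable efficacy endpoint. Its four coarse covariates were chosen for persistence and adherence, not for AEs, and time on treatment may still differ. All of this stands. A reader might infer that the matched tables should become the sole basis for between-drug statements; these limits do not allow that.

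Fourth, a reader might infer that a 66% match rate shows a sizeable imbalance in AE-related factors. It does not. It is a planning assumption, the achieved rate also depends on the caliper and on Full Analysis Set exclusions, and patients can go unmatched for reasons unrelated to AE risk.

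**Conclusion.** The point holds as a gap in presentation with a cheap remedy. AEs are shown by drug in the Treated Set only, the plan expects the groups to differ, and the cohort built to handle this is not used for AEs. Patient mix can therefore appear as a drug difference.

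A reader might go further and conclude that patient mix will distort the AE tables, or that the plan makes an invalid safety comparison. The documents support neither. They say only that differences may be expected, they give no size or direction for AE-related factors, and they plan no comparative safety analysis.

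The one figure resting on the plan's numbers is that 544 of 1600 patients (34%) in the AE tables would be outside the matched cohort. The risk ratios, 1.08 to 1.26 at 67% v 33% and 1.08 to 1.43 over the other unequal mixes, are illustrations on assumed risks and shares.

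**What to change.** 1. Keep the Treated Set AE tables as the complete safety record. Head them as unadjusted and not a comparison of the drugs.
2. In SAP Table 6.3: 1, also tick the matched group for safety endpoints. In SAP 7.8, repeat the overall AE summary, the serious AE table and the table of AEs leading to discontinuation by drug in the matched cohort, as a supplementary analysis.
3. State that any between-drug remark refers to the matched tables and gives their limits: about 1056 of 1600 patients, drawn from the Full Analysis Set, four coarse matching covariates, and time on treatment that may differ between drugs.
4. While editing SAP 7.8, replace the term safety population with Treated Set, if that is what is meant.

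Cost: a few lines of SAP text and a re-run of existing table programs on a set already defined. Rare events are estimated less precisely in the matched cohort, which is a further reason to keep the Treated Set tables.
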